A total of 60 bipolar and healthy comparison subjects (n=30 per group, 21-26 years of age, 50% women, with no history of a severe AUD) will be recruited from the greater Austin area. We included individuals with a history of mild/moderate AUDs as doing so is more generalizable since it is common that individuals in this age group experiment with alcohol use. We will exclude individuals with a history of symptoms suggesting dependence (which is what you see in individuals with severe AUDs). Subjects will be recruited through multiple venues to optimize subject enrollment. Once recruited and enrolled, subjects will undergo detailed structured clinical evaluations to verify inclusion and exclusion criteria followed by structural MRI assessments. Following standard beverage administration procedures, they will then complete measures of subjective response to alcohol and fMRI scans while under the influence of alcohol or a placebo condition (counter-balanced). All subjects will be euthymic and alcohol/placebo sessions will occur within 3 days of each other. fMRI assessments will include a continuous performance task with emotional and neutral distractors (CPT-END) and resting state scans. Participants will first complete the CPT-END task at baseline (outside the scanner) before their alcohol or placebo session. Our recent data suggest differences in ventral brain networks when viewing emotional stimuli for the first time compared to the second time (associated with habituation of emotional networks), but that there are minimal differences between the second and third viewings. We will investigate (Aim 1) differences in subjective response to alcohol between bipolar and healthy participants and associations with recent drinking patterns and (Aim 2) differences between bipolar and healthy young adults in alcohol-induced changes, compared to placebo, in regional activation in vPFC emotional networks and connectivity among these regions.

4 Data Analysis

Describe the data analysis plan, including any statistical procedures or power analysis.

To input text, click in the light grey area below.

Aim 1: Between Group Differences in Subjective Response to Alcohol

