Group (bipolar, healthy)-by-condition (alcohol, placebo)-by-time of subjective response interactions on subjective response to alcohol will be modeled, covarying beverage condition order, biological sex, and age with SEAS and DEQ subscale scores as the dependent variables. Time of subjective response (pre- and post-scan) and beverage condition (alcohol, placebo) will be within-subject factors and group an independent between-subject factor. Following no group-by-condition-by-time of subjective response interaction, the three-way interaction term will be dropped and group-by-condition interactions investigated. Following no two-way interaction, the two-way interaction term will be dropped and main effects of group and condition assessed. Findings for these planned analyses will be considered significant at $p < 0.05$.

Between Group Differences in Functional Connectivity to Alcohol

Using the CONN Toolbox, we will perform region of interest (ROI)-to-ROI bivariate correlation first-level analysis to calculate fisher transformed correlation coefficients (measure of functional connectivity (FC)) between a priori ROI-to-ROI connections during placebo and alcohol condition CPT-END fMRI sessions. We will extract Fisher transformed correlation coefficients between ROI-to-ROI connections during emotional stimuli and during squares for analysis. We will calculate the contrast: FC during emotional stimuli minus FC during squares for alcohol and placebo conditions, in line with prior studies. A priori ROIs will be defined using the FSL Harvard Oxford Atlas in the CONN toolbox, and included bilateral insula, amygdala, nucleus accumbens (NAcc), ventromedial PFC (vmPFC), lateral orbitofrontal cortex (OFC), subcallosal cortex (SCC), and inferior frontal gyrus pars triangularis (IFG.tri). We will examine ROI-to-ROI connections between limbic/subcortical regions (insula, amygdala, or NAcc) with ventromedial PFC (vmPFC or SCC) and ventrolateral PFC (OFC or IFG.tri) regions.

We will use a mixed model to examine group by condition by hemisphere (left, right) interactions on ROI-to-ROI FC response to emotional stimuli (contrast: emotional stimuli - squares). Group will be an independent between-subject factor, condition and hemisphere within-subject factors, and ROI-to-ROI FC the dependent variable. Results of primary models will be considered significant at $p \leq 0.004$ (Bonferroni correction for twelve ROI-to-ROI connections).

STUDY PROCEDURE DESCRIPTION

5

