- The *Hamilton Anxiety Rating Scale (HAM-A)* and *Hamilton Depression Rating Scale (HAM-D)*: clinician-administered scales validated for assessing anxiety and depression in adolescents and adults [25, 26]. *The Young Mania Rating Scale (YMRS)*: an 11-item clinician-administered scale validated for both children and adults to quantify manic symptoms [27]. These measures are used to assess mood symptoms over the last week at the time of baseline clinical assessment.

- Additionally, mood state will also be measured by self-report surveys, i.e. the *Beck Depression and Anxiety Inventories* [28, 29]. These self-report surveys will be completed before beverage consumption during the alcohol and placebo MRI sessions.

Assessment for Ferromagnetic Objects: Participants will be carefully screened for implanted devices and previous exposure to metallic fragments. Screening involves verbal discussion with the researcher (and/or Safety Officer), as well as completion of a checklist maintained by the Imaging Research Center. All ongoing participants will be required to fill out a screening form at the beginning of their participation, after every revision to the form's criteria, at the beginning of every semester, and after any changes to their medical/health status that may be relevant to MRI safety. Subjects having or suspected of having foreign metal objects will be excluded. This exclusion may be confirmed, with a subject's consent, either by obtaining and examining the subject's medical chart and/or contacting their physician if there is any question.

Assessment of Pregnancy: The risks of study with pregnancy and the possibility of pregnancy will be discussed with each menstruating female subject by an investigator of the study. A urine screening will be required for all female subjects with childbearing potential within 24 hours prior to scanning to verify

pregnancy status. Pregnant women will be excluded from participating in this protocol. If there is any question that a pregnancy could exist, but is at too early a stage for detection by this test, the woman will also be excluded from study.

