Beverage Manipulation and Procedures: Participants will use alcohol free mouthwash prior to the first breathalyzer test. Participants will be assigned randomly to the placebo or alcohol condition. Participants are told they will complete two alcohol sessions where they will be assigned a large dose of alcohol (alcohol condition) or a small dose of alcohol (placebo condition). These will be counter-balanced. A placebo condition will be used to model effects of alcohol expectancies. Using standardized alcohol administration procedures, study staff who are blind to beverage condition will calculate individual dose based on the participants' gender and weight, and will pour drinks from vodka bottles in full view of participants. Participants will be given 10 minutes to consume each of two beverages (20 minutes total time drinking) containing a 1:3 mixture of 80 proof vodka (mean: 2.389 ml/kg of body weight; women: 2.174 ml/kg of body weight) to mixer (diet 7-up, cranberry juice, and lime juice) to achieve a target breath alcohol concentration (BrAC) of 0.08%. In the placebo condition, the vodka bottle will contain decarbonated tonic. Consistent with standard procedures [35], the rims of the glasses will be moistened with vodka, and a squirt of 100 proof alcohol from a plastic lime juice container will be added to the top of each drink just prior to serving.

6

Research Participant Information

Describe the research population.

**For multiple research populations (e.g., teachers, students, and parents), copy this section as necessary to describe your population.*

a Participant Group Name

To input text, click in the light grey area below.

Participants include young adults diagnosed with bipolar disorder and typically developing young adults.

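### Aim 1 lists order, sex and age as covariates without crossing them with condition; read as main effects, they leave the group-by-condition and three-way tests unadjusted

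*Combined protocol and SAP*

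**What the plan says.** Section 4 (Data Analysis, Aim 1) models the SEAS and DEQ subscales at two times in each of two beverage conditions, "covarying beverage condition order, biological sex, and age with SEAS and DEQ subscale scores as the dependent variables". Time and "beverage condition (alcohol, placebo) will be within-subject factors and group an independent between-subject factor".

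Testing is stepwise: "Following no group-by-condition-by-time of subjective response interaction, the three-way interaction term will be dropped and group-by-condition interactions investigated". If that is also absent, "the two-way interaction term will be dropped and main effects of group and condition assessed". The threshold is 0.05, with sidedness not stated. Every interaction named is among group, condition and time. No covariate is crossed with anything, and the coding of order is not given.

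Other relevant text:
- Section 3 gives 30 per group, half women, aged 21 to 26, with the two beverage sessions counter-balanced and within 3 days of each other.
- Section 2 says the groups are matched on age and sex. Order is not mentioned there.
- Section 5 (Beverage Manipulation and Procedures) says condition is assigned at random. Neither it nor Section 3 promises balance of order within diagnostic group.

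**The concern.** Hypothesis (a) in Section 1, a low response to alcohol in bipolar disorder, is carried by the interaction tests, because response to alcohol here means alcohol compared with placebo within a person. A covariate helps such a test only if it can explain why that within-person difference varies between people. A main effect of sex says that women rate higher or lower in every session. It does not let the alcohol-placebo difference depend on sex. The same holds for age and for order as a sequence.

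The plan therefore appears to adjust its key tests for session order, sex and age but, on the plain reading, does not. Any variation in alcohol response from those sources stays in the error term. If the two groups happen to differ in the share who had alcohol first, an effect of session position passes into the group-by-condition estimate.

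**Working it through.** **1. The plan's own power figure.** Section 8 states more than 80% power at alpha 0.05 for a between-group d of 0.7 with 30 per group. By the normal approximation, 0.7 × √(30/2) = 2.711.
- Two-sided: 2.711 − 1.960 = 0.751, giving 77.4% (76.0% by noncentral t).
- One-sided: 2.711 − 1.645 = 1.066, giving 85.7% (85.0% by noncentral t).

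The figure is met one-sided only. That is a separate matter, but it shows there is no spare precision in a two-sided test.

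**2. The algebra.** For person i, condition c and time t:

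Y(i,c,t) = terms in group, condition and time + b1·order(i) + b2·sex(i) + b3·age(i) + person effect + error.

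Alcohol minus placebo subtracts the same b1·order(i) + b2·sex(i) + b3·age(i) from itself. So does the change in that difference from pre- to post-scan. This needs no assumed effect size.

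**3. Numerical check.** Mixed models were fitted to one simulated data set of 60 people × 2 conditions × 2 times. The true group-by-condition effect was zero. Assumed effects of session position (0.8), sex and age on response were built in, with order split 12:18 in one group and 18:12 in the other.

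| Covariates | Group-by-condition (SE) | Three-way (SE) | Group main effect |
|---|---|---|---|
| None | 0.534 (0.362) | −0.127 (0.286) | −0.325 |
| Main effects | 0.534 (0.362) | −0.127 (0.286) | −0.297 |
| Crossed with condition and time | 0.231 (0.281) | −0.004 (0.291) | −0.297 |
| Order as session number | 0.172 (0.286) | −0.127 (0.286) | −0.316 |

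Main-effect covariates move only the group main effect. The expected shift from the built-in imbalance is 0.8 × 2 × (0.6 − 0.4) = 0.32; crossing moved the estimate by 0.534 − 0.231 = 0.303. With 8 of 60 alcohol sessions deleted, cancellation was near-exact (0.491 without covariates, 0.484 with main effects).

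**4. Cost in power.** Simulated alcohol-minus-placebo differences: 30 per group, sex 15/15 per group, group difference 0.7 SD, two-sided 0.05. The documents give no covariate effects, so the share of variance explained is an assumption.

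| Share explained | Order balance | Power, main effects | Power, crossed |
|---|---|---|---|
| 0% | within group | 76.1% | 75.4% |
| 0% | overall only | 76.2% | 74.5% |
| 10% | within group | 76.8% | 79.5% |
| 10% | overall only | 76.4% | 78.4% |
| 20% | within group | 77.6% | 84.3% |

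As a check, removing a share R of the variance raises the effective d to 0.7/√(1−R): 0.738 at 10% and 0.783 at 20%. By noncentral t on 55 degrees of freedom these give 80.2% and 84.6% under perfect balance, just above the simulated values.

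**5. Type I error, order balanced within group.** With main effects it was 4.4% at 10% explained and 3.6% at 20%, against 5.2% and 4.9% with crossed terms. The test is conservative because balance removes order and sex variation from the group comparison while the standard error still contains it.

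**6. Order not balanced within group.** If 30 of 60 have alcohol first overall, a split of 12:18 against 18:12 or worse arises in about 20% of allocations. At that split an order effect of ±k SD on the difference shifts the group contrast by k × 2 × (0.6 − 0.4) = 0.4k, that is 0.10, 0.20 or 0.30 SD for k = 0.25, 0.5 or 0.75. Simulated type I error was about 6%, 8% and 9%.

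**The case against.** **The model is not fully specified.** Section 4 gives no equation, software or coding for Aim 1, and its wording also fits repeated-measures ANCOVA. Software that crosses covariates with the within-subject factors would adjust both interactions. Order coded as session number varies within person and would adjust group-by-condition, though not the three-way estimate (step 3). This stands as a limit. The step-down rule, which lists and drops only design terms, favours the main-effects reading without settling it. The ambiguity is itself a reason to state the terms.

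**The groups are matched and order is counter-balanced.** Matching limits bias from age and sex but leaves their variance in the error term. Order is not said to be matched or stratified by group.

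**The gain is modest and could be negative.** This stands. The 10% and 20% shares are assumptions, and with no covariate effect the added terms cost a little power.

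**Sex-specific volumes.** A reader might infer that the sex-specific beverage volume itself creates a sex difference in response. The documents do not support that. Section 5 adjusts the volume for gender and weight to reach a common target breath alcohol concentration, and takes the first rating once ascending BrAC reaches 0.06%. The dosing rule aims to equalise exposure.

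**Conclusion.** The concern holds in this form. On the plain reading, the Aim 1 covariates adjust only the fallback group main effect and not the two interaction tests that carry hypothesis (a). The cancellation is exact with complete data, close to exact with some missing sessions, and independent of any assumed effect size.

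The practical size is modest: about 2 to 3 points of power forgone at an assumed 10% of variance explained and 6 to 7 points at 20%. If order happens to be unbalanced between groups, its effect is also left in the estimate.

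Three stronger conclusions are tempting and should not be drawn:
- That the covariates are useless. They still adjust the group main effect.
- That the analysis is biased. With order balanced within group there is no bias. With random order the bias depends on the split that happens to arise, and averaged over random allocations simulated type I error stayed near 5%.
- That the test necessarily runs below 5%. That requires order to be balanced within each group, which the documents do not promise; at the 12:18 split the error goes the other way.

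The point concerns Aim 1 only. The connectivity model in Section 4 names no covariates.

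**What to change.** In Section 4, Aim 1, define order as sequence (alcohol-first or placebo-first). Add order-by-condition, sex-by-condition and centred-age-by-condition terms, each also crossed with time for the three-way test. State that the covariate-by-condition terms stay in the model when the three-way design term is dropped.

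An equivalent person-level form uses two regressions:
- **Group-by-condition:** regress each participant's time-averaged alcohol-minus-placebo score on group, order, sex and age.
- **Three-way:** regress the post-minus-pre-scan change in that difference on the same terms. The first regression does not cover this test.

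The cost is a short addition to the analysis section and three degrees of freedom per contrast (58 to 55). In the full hierarchical model, crossing three covariates with condition, time and condition-by-time adds 3 × 3 = 9 fixed terms. If the covariates explain nothing, about 1 to 2 points of power are lost. No new data are needed.

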Official title: Subjective Response to Alcohol and Associated Neural Systems in Bipolar Disorder

NCT number: NCT04063384

Document last approval date: 8/28/2023

Document information: Overall study protocol and change in behavior and functional connectivity (primary outcomes) statistical analysis approach.

1 Research Hypothesis

To input text, click in the light grey area below.

We hypothesize that:

- a) Individuals with bipolar disorder will show a low response to alcohol (decreased self-report of feeling intoxicating and experiencing stimulating/sedative effects of alcohol) and a low response to alcohol will be associated with higher alcohol intake.
- b) Individuals with bipolar disorder, compared to healthy comparison subjects, will show smaller alcohol-induced changes in regional responses of, and functional connections between, the amygdala, striatum, and the dorsal and ventral prefrontal and anterior cingulate cortices. Smaller change in regional responses of, and functional connections between, these regions will be associated with a self-reported low level of response to alcohol.

2 Study Background

To input text, click in the light grey area below.

Disease progression in bipolar disorder is very heterogeneous and our understanding of mechanisms associated with differences in disease progression is limited. Bipolar disorder has a high rate of comorbidity with alcohol use disorders (AUDs) [1-3], with estimates as high as 60% [4]. Comorbidity with AUDs is related to more severe illness outcomes in bipolar disorder, including increased impulsive risk-taking [5-8], more severe mood episodes [9, 10], cognitive deficits [11-13], decreased quality of life and a higher risk for suicide [14-17]. These associations highlight the importance of understanding how this comorbidity develops and the relationship with disease progression in bipolar disorder. However, there has been little study in this area; neuroimaging studies in bipolar disorder have not focused on alcohol use, and related differences in disease progression and, in fact, often exclude subjects with this comorbidity from study.

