Participants will consume their beverages in a private interview room at the BIC in the Health Discovery Building. A study staff member will be present at all times. Following 10 minutes for absorption, breathalyzer tests will be conducted until the participant reaches an ascending limb BrAC of 0.06%, at which time the first alcohol response measures will be collected (e.g. *Subjective Effects of Alcohol Scale*). Immediately following, participants will complete their MRI assessment. This is done to ensure we are imaging during the ascending limb of the BAC. For this study, we are focusing on imaging during the ascending limb of the BAC based on our pilot suggesting altered sensitivity to the stimulating, but not sedatative, effects of alcohol in bipolar disorder.

The MRI scan session will last approximately 30 minutes. Subjects will complete a neuropsychological task (i.e. the CPT-END). For each individual completing the alcohol and placebo sessions, functional MRI data during the alcohol session will be directly compared to placebo fMRI data.

Following scanning, the participant will be escorted back to a private interview room and subjects will immediately be given a breathalyzer test and BrAC recorded. They will complete alcohol response measures again). Participants will be escorted to a comfortable private room in the PI's research suite where they can watch television while they detox. Consistent with NIAAA guidelines for human alcohol studies, BrAC readings will be taken every 30 minutes until participants are below 0.04% at which time they will be allowed to leave the laboratory.

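### Aim 1 tests several SEAS and DEQ subscales, not listed in the document, each at p < 0.05 with no correction across them, while connectivity is Bonferroni-corrected

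*Combined protocol and SAP*

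**What the plan says.** The document information line at the front describes the statistical approach for "change in behavior and functional connectivity (primary outcomes"), so behavior and connectivity share that label. Hypothesis (a) in Section 1 predicts a low response to alcohol ("decreased self-report of feeling intoxicating and experiencing stimulating/sedative effects of alcohol").

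Section 4 (Data Analysis, Aim 1) fits group-by-condition-by-time models "with SEAS and DEQ subscale scores as the dependent variables". If there is no three-way interaction, "the three-way interaction term will be dropped and group-by-condition interactions investigated". The next step reads: "Following no two-way interaction, the two-way interaction term will be dropped and main effects of group and condition assessed". One rule covers the sequence: "Findings for these planned analyses will be considered significant at" p < 0.05. The section does not list or count the subscales, name a lead, or say how many must be positive to support hypothesis (a).

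The connectivity part of Section 4 sets p ≤ 0.004 ("Bonferroni correction for twelve ROI-to-ROI connections"). The power statement in Section 8 uses alpha = 0.05 with no allowance for several subscales.

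**The concern.** Both outcomes carry the primary label and both are measured by several variables, but only connectivity has a rule for that. As written, an Aim 1 finding can be declared on whichever subscale falls below 0.05, with no account taken of the others. The false-positive rate for the aim then grows with the number of subscales scored, and a reader of the results could not tell from the plan how many chances there were. Subjective response is also the only behavioral analysis for which Section 4 specifies a model, so this rule determines what can be claimed for the behavioral outcome.

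**Working it through.** **The plan's own figures.** Connectivity: 3 limbic/subcortical regions × 4 prefrontal regions = 12, and 0.05/12 = 0.00417, stated as 0.004. The correction matches its count. Power: with 30 per group, d = 0.7 and alpha 0.05, the noncentral t (df 58, noncentrality 0.7 × √(30/2) = 2.71) gives 76.0% two-sided and 85.0% one-sided. The stated figure above 80% is reached only one-sided, and the document does not state sidedness. That is a separate matter; 76% is the baseline used below.

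**Inputs for the error rate.** Per-test alpha 0.05 (Section 4). The number of subscales k is not in the document. I take k = 2 (the fewest that two instruments imply), k = 3 (the constructs in hypothesis (a)) and k = 6 (illustrative). Correlation between subscales is also not given, so I take 0.9 to 0. All nulls are true, tests are two-sided, and any subscale counts.

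**One interaction term, uncorrected.** With independent subscales the chance of at least one false finding is 1 − 0.95^k. Correlated cases are simulated with equicorrelated normal test statistics.

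| k | correlation 0.9 | 0.5 | 0 (exact) |
|---|---|---|---|
| 2 | 7.0% | 9.1% | 1 − 0.95² = 9.75% |
| 3 | 8.4% | 12.5% | 1 − 0.95³ = 14.3% |
| 6 | 10.8% | 20.8% | 1 − 0.95⁶ = 26.5% |

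Strong correlation reduces the excess but does not bring it to 5%.

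**Holm across subscales within one term.** When all nulls are true, a false finding requires the smallest p-value to be at or below 0.05/k.

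- k = 3: 1 − (1 − 0.05/3)³ = 4.9% at correlation 0, and 3.0% at 0.9.
- k = 6: 1 − (1 − 0.05/6)⁶ = 4.9% at correlation 0, and 2.1% at 0.9.

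If the two interaction terms are independent, the error across both is 1 − (1 − e)², where e is the error per term. For k = 3 this is about 6–10%, and for k = 6 about 4–10%. A single lead subscale at 0.05 per term gives 1 − 0.95² = 9.75% across both.

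**Power at the strictest Holm step** (noncentral t, df 58, two-sided):

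| alpha | d = 0.7 | d = 1.0 | d = 1.3 |
|---|---|---|---|
| 0.05 (uncorrected, or lead subscale) | 76% | 97% | >99% |
| 0.05/3 = 0.0167 | 60% | 92% | 99% |
| 0.05/6 = 0.0083 | 50% | 87% | 99% |

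The range 0.7 to 1.3 is the pilot between-group effect in Section 8. Its application to the interaction contrasts is an assumption; the document does not say so.

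**The case against.** The best defence is that the error rates depend on a decision rule the plan never states. Hypothesis (a) is directional and joins its constructs with "and". If only results in the predicted direction counted, the chance on one term with independent subscales would be 1 − 0.975³ = 7.3% for k = 3 and 1 − 0.975⁶ = 14.1% for k = 6, falling to about 4% and 5% at correlation 0.9. If every construct had to be significant, it would not exceed 5%. This stands as a limit on the size. It does not remove the point, because the plan adopts neither rule and its p < 0.05 applies to each analysis.

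Four stronger readings are tempting, and the document does not support them.

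- **The headline should be the error over both interaction steps** (16–26% with 3 subscales, 21–46% with 6). Testing two terms in sequence does add error. But the plan's own comparator corrects across connections, not across model terms, so it supports correction across subscales only.
- **The subscales were left open to later choice.** The document shows only that they are not listed here. Two instruments are named, the wording reads naturally as all their subscales, and the text refers to appendices that are not in this file.
- **Subjective response is the only behavioral analysis.** Sections 1, 3 and 8 also name associations with drinking. What can be said is that it is the only one with a specified model. Section 4 also reserves the term primary models for connectivity.
- **The group main effect should be demoted.** Pooled over alcohol and placebo, it cannot isolate response to alcohol. That is a question of interpretation, not multiplicity, and nowhere is a group main effect said to support hypothesis (a).

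**Conclusion.** The point holds, limited to correction across subscales. A primary-labelled outcome is tested on several subscales at p < 0.05 each, with no list, lead or correction in the available document, while the other primary outcome is corrected. On a single interaction term the chance of at least one false finding is 7–10% with 2 subscales, 8–14% with 3 and 11–26% with 6. These figures rest on assumed counts, correlations from 0.9 to 0, two-sided tests and an any-subscale rule. They would be lower under a directional or all-constructs rule. Nothing elsewhere cures the gap: the pilot remark on stimulation in Section 5 is used to justify scan timing, not to choose a lead outcome. This should be settled in the analysis plan; it does not undermine the design.

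**What to change.** In Section 4, list the SEAS and DEQ subscales to be tested and adopt one of two rules.

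(a) Apply Holm across the listed subscales within each interaction term to decide which findings are declared significant, parallel to the connectivity correction. Keep the family at the full list for both terms, and state that error across the two terms is then about 4–10%.

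(b) Name one lead subscale in advance at 0.05 and make the others secondary. Section 5 (Laboratory Alcohol Challenge Procedures) offers a basis for stimulation, since the pilot suggested "altered sensitivity to the stimulating, but not sedatative, effects of alcohol in bipolar disorder". State that error across the two terms is up to about 10% here as well.

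Under either rule, leave p < 0.05 as the criterion for dropping model terms. A stricter criterion there would make it easier to discard a real interaction; the correction should govern claims, not model selection.

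The change is to wording, but (a) has a real cost. At d = 0.7, power at the strictest step falls from 76% to 60% with 3 subscales and to 50% with 6. Restoring 80% would take about 43 or 50 per group, against 33 uncorrected (normal approximation, 2(z₁₋α/₂ + z₀.₈)²/0.7²); the plan has 30. At d = 1.0 power stays at 92% and 87%. Option (b) costs the lead subscale no power, but the remaining subscales can then support only secondary statements.
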